Investigator Studies Program (MISP) Protocol Template

Requirements for Submitting a Full Proposal

Section #1 - MISP Protocol Identification

Study Title:	A pragmatic trial of secondary prophylaxis with Bezlotoxumab to prevent C. difficile relapse among hospitalized adults receiving antibiotics.
Request Date:	August 31,2018
Institution Name	Montefiore Medical Center
Investigator Contact Information: Full address Phone No. Fax No. e-mail address	[name] [name] Division of Infectious Disease/AIDS Center [name] [contact] [contact] [contact]

[figure not shown]
Section #2- Core Protocol	
2.1 Objectives & Hypotheses	
2.1 Objectives:
 
 A. Can monoclonal antibody treatment active against C. difficile toxin B (Bezlotoxumab) prevent relapse of CDI (C. difficile infection) among patients recently infected with C difficile, with resolved CDI after completing standard C difficile therapy, but receiving subsequent antibiotics for other infections? B. Does stool carriage of C difficile after end of CDI treatment predict relapse? If so, are failures of CDI prophylaxis due to reinfection or relapse with the same strain? 
2.1.1 List the clinical hypotheses.
 
 A. Antibody active against C. difficile toxinB (Bezlotoxumab) can prevent relapse of C. difficile disease (CDI), when patients recently affected by CDI are prescribed antibiotics for other indications. B. Failures of CDI prophylaxis, if found, are due to persistent carriage of C. difficile, rather than acquisition of a new strain.
2.2 Background & Rationale, Significance of Selected Topic & Preliminary Data	
Clostridioides difficile infection (CDI) is the leading hospital-acquired infection in the US, affecting nearly 500,000 persons annually, and killing 29,000. Of concern, 83,000 patients or ~20% have relapsing disease with an estimated healthcare cost of \$13,500 – 18,000 per relapse (Lessa, 2015). Some of these relapses can continue to recur whenever treatment is stopped. The main risk factor for CDI relapse after resolution of symptoms is further antibiotic exposure (Despande, 2015) as this is believed to disrupt the intestinal microbiome favoring regrowth of C difficile.
 
Attempts to attenuate the risk of CDI relapse include prolonged use of CDI-active therapy, fecal microbiota transplant (FMT) and monoclonal antibodies targeting C. difficile toxins. Retrospective studies by Van wise (2016) and Wong (2015) , including nearly 500 patients showed CDI relapse rates in a population of recent CDI patients receiving further antibiotics could be reduced from 20-27% to 4-8% with oral vancomycin and/or metronidazole. Another study showed no benefit of oral vancomycin prophylaxis after a first episode of CDI (Carignan, 2016). Fidaxomicin may be even better in this regard due to its more selective effect on the microbiome leading to fewer relapses after initial treatment (15% relapse with fidaxomicin vs. 25 % for vancomycin)(Louie,2011; Fidaxomicin Package Insert). In initial CDI therapy where concurrent antibiotics were also used in this trial, Fidaxomicin still demonstrated less relapse than oral vanco,17% vs. 26% [Mullane,2011] Finally, prophylactic fidaxomicin use prevented C difficile in high risk oncology patients, all of whom also received other antibiotics(rate of confirmed CDI was 4% vs. 10% with placebo) (Mullane, 2018). Nonetheless, the recent Infectious Disease Society of America statement on CDI (published 3/2018) indicates the following: “There are insufficient data at this time to recommend extending the length of anti-C. difficile treatment beyond the recommended treatment course or restarting an anti-C. difficile agent empirically for patients who require continued antibiotic therapy directed against the underlying infection or who require retreatment with antibiotics shortly after completion of CDI treatment, respectively (no recommendation)”. FMT has shown promising efficacy in frequent CDI relapsers (Moayyedi, 2017) but is cumbersome, there is no FDA-approved regimen, and there are potential long-term adverse side effects as the intestinal microbiota has been associated with colon cancer, diabetes, obesity, and atopic disorders such as asthma.


	
Bezlotoxumab is an FDA-approved monoclonal antibody targeting the pathogenic major toxin B of C. difficile, which has been shown in the MODIFY trials to reduce the risk of recurrent CDI from 27 to 16% when used concurrently with primary CDI therapy (Merck, Zinplava Package Insert, Wilcox, 2017). In these pivotal studies, 35-42% of subjects (in different treatment groups) had concurrent antibiotics with CDI therapy, and ~35% continued antibiotics beyond their CDI therapy (Wilcox, appendix, 2017). The efficacy of bezlotoxumab in this high-risk group for relapse has not been specifically reported; nonetheless, bezlotoxumab was effective in other high-risk groups including older age (>=65), the immunocompromised, and those with more than 1 prior CDI or severe CDI.
 
While Bezlotoxumab was approved for use during an episode of CDI concurrent with standard-of-care CDI-active antibiotics, there is no reason to expect it would not work in the high-risk setting proposed here – inpatient subjects with recently treated CDI (within the past 90days) receiving subsequent courses of antibiotics for non-CDI indications. This cohort of patients at our institution has a 20.8% rate of CDI (Wong, 2015) which is increased to 26.7% if age of >=60 is used as a cutoff (unpublished data). Birch et al (2018) showed that within the MODIFY trials, the timing of Bezlotoxumab use relative to the start of CDI-active antibiotics (a 10-14day window) had no bearing on its efficacy; its half-life of 19 days means that it provides protection over the course of the 12-week observation period after the start of CDI therapy. This proposal suggests expanding the utilization of bezlotoxumab to a 14-90 day (~2-12 weeks) window after initial CDI therapy, if and when other antibiotics with a propensity for inducing CDI relapse are utilized. A single dose of bezlotoxumab in this setting would not affect the risk for CDI acquisition or relapse, but should attenuate the clinical consequences of this occurring by neutralizing the pathogenic toxin B, to a similar extent as in the MODIFY trials. In fact, it may work more efficiently as the highest levels of antibody will be available during the highest risk period for relapse –concurrently or shortly after use of CDI-inducing antibiotics.

2.3 Study Design	
This proposal uses a prospective cohort of CDI patients, 60 years of age and older, admitted to 2 sites of 1 Medical Center, and receiving “other” antibiotics, within 14-90 days of their CDI diagnosis.
 
These patients will be identified by a bioinformatics approach, using Clinical Looking Glass software developed at our medical center. All inpatients 60 years old or above, with a CDI laboratory diagnosis within 14-90 days of the present date will be assessed for use of antibiotics at high-risk for inducing CDI, as well as any concurrent C. difficile active antibiotics (“prophylaxis”). In addition, all new admissions to our hospital with a CDI diagnosis within 12 months are flagged for infection control purposes, and these patients will also be assessed for qualification into the study. Inclusion criteria are :
 
 1. CDI within 90 days 2. Use of high-risk antibiotics for inducing CDI within 72 hrs. of enrolment 3. No use of CDI active antibiotics within 24 hrs. 4. Able to sign consent for the study, or have an identified surrogate. 
As this is a pragmatic study, reflecting mostly standard medical care, there are few exclusion criteria :
 
 1. Prior CDI episode was felt to be colonization after chart review; 2. Subject not expected to survive 8 weeks (based on PI impression or chart review, considering factors including end-stage cancer, CHF, sepsis with high pressor requirement); 3. Documentation of current diarrhea (3 or more unformed stools per day) at time of enrollment, possibly due to CDI. 4. Receipt of prior fecal microbiota transplant or prior bezlotoxumab. 5. Congestive heart failure, as this diagnosis demonstrated increased mortality in the

	
MODIFY studies with bezlotoxumab vs. placebo (Zinplava Package insert).
 
Those patients meeting the study inclusion/exclusion criteria will be offered open-label Bezlotoxumab infusion. This active intervention arm will have baseline stool samples collected for C difficile culture and typing at study entry and upon CDI relapse, if any
 
The comparator groups will be
 
 1. The historical control group from the Wong study, and 2. A concurrent observational arm – consisting of those patients otherwise eligible for the study, but : 
 A. Not consenting to study enrolment, and B. Taking no form of CDI prophylaxis (no oral vancomycin, metronidazole or fidaxomicin use as defined below). 
All cohort members will be subject to standardized chart review for baseline parameters at study entry, and structured followup by chart review every 2 weeks for 8 weeks for CDI relapse (the primary endpoint), tolerability of study drug (if administered) , length of hospitalization/ICU stay or death.
 
Use of CDI prophylaxis will be adjudicated to see if it conforms to the standards established in the Wong study – prophylaxis used for at least 50% of the duration of the concomitant antibiotics course and at least up to 72 hrs before the end of the concomitant antibiotics. Patients receiving any such prophylaxis will be excluded from the per-protocol analysis, which will be the primary analysis. Secondary analysis will also be performed on an intent-to-treat basis, where group assignment is determined based on use of prophylaxis at study entry only.
 
This design was chosen to parallel that of the retrospective Wong study at our same site – to allow comparisons with the historical treatment groups in that study.

2.4 Study Flowchart
	<pre> graph TD Cdiff_dx[14-90 days Cdiff dx] --> Inpatient Inpatient --> On_Abx{On Abx?} On_Abx -- No --> Follow_daily[Follow daily] On_Abx -- Yes --> On_CDI_ppx{On CDI ppx?} On_CDI_ppx -- Yes --> Offer_Bezlo[Offer Bezlo Study] Offer_Bezlo --> Enrol[Enrol] Offer_Bezlo --> Cdiff_Cx[C diff Cx and f/u 8 wks] On_CDI_ppx -- No --> Decline[Decline] Decline --> Follow_8_wk[Follow for 8 wk] Follow_8_wk --> Relapse_no_ppx[Relapse, no ppx No Relapse, no ppx] Follow_8_wk --> Relapse_Bezlo[Relapse, Bezlo No Relapse, Bezlo] </pre>

2.5 Study
	
STUDY DESIGN

Procedures	
This prospective cohort study will be conducted using inpatients at the 1044 adult medical/surgical-beds on 2 campuses of the Montefiore Medical Center in the Bronx, New York. No work on this study will proceed until it is approved by our local Institutional Review Board.
 
SUBJECT IDENTIFICATION –INCLUSION CRITERIA
 
All patients with a laboratory diagnosis of CDI initially diagnosed within 3 months of screening, who are getting an order placed for inpatient antibiotics will be identified by bioinformatics—and will be eligible for study entry. They will be screened for concurrent use of metronidazole, oral vancomycin or fidaxomicin –if present; they will be rescreened for inclusion if further antibiotics are given without concurrent prophylaxis. If no prophylaxis is identified, then their providers will be approached to consider enrolling the patient into the current active arm for open-label Bezlotoxumab.
 
Inclusion criteria are :
 
 1. CDI within 90 days 2. Use of high-risk antibiotics for inducing CDI within 72 hrs of enrolment 3. No use of CDI active antibiotics within 24 hrs 4. Able to sign consent for the study, or have an identified surrogate. 
EXCLUSION CRITERIA
 
As this is a pragmatic study, reflecting mostly standard medical care, there are few exclusion criteria :
 
 1. Prior CDI episode was felt to be colonization after chart review(any physician-identified diarrhea is allowed, but not testing of asymptomatic patients such as test-of-cure testing or admission screening); 2. Subject not expected to survive 8 weeks; 3. Documentation of current diarrhea (3 or more unformed stools per day) at time of enrollment, possibly due to CDI. 4. Receipt of prior fecal microbiota transplant since the last CDI episode, or planned at time of screening or prior bezlotoxumab. 5. Congestive heart failure, as this diagnosis demonstrated increased mortality in the MODIFY studies with bezlotoxumab vs. placebo (Zinplava Package insert). 
CLINICAL DATA COLLECTION
 
Data on included patients will be collected by medical record review both manually and by using Clinical Looking Glass (CLG) software. Clinical data collected consists of patient demographics, comorbidities by ICD10 codes, length of hospital stay, nursing home residence, all antimicrobial agents received, use of proton pump inhibitors or histamine-2 blockers, all prior C. difficile assays, and severity of CDI markers on the date of CDI diagnosis – maximum temperature, maximum WBC, maximum creatinine, serum albumin –in order to calculate a Zar severity score (Zar, 2007). Manual chart reviews will be performed of all antibiotic courses for 8 weeks from enrollment and to assess for signs of CDI relapse, including symptoms such as abdominal pain or diarrhea as well as physical findings, vital signs, white blood cell, microbiologic data including both positive and negative C. difficile assays, and radiographic data. Particular weight will be given to assessment by infectious disease specialists, if consultation is performed.
 
DEFINITIONS
 
A valid high risk antibiotic course is defined as:
 
 1. Consisting of a beta lactam, carbapenem, quinolone, clindamycin, macrolide, or polymyxin, AND 2. Starting as early as 14days after the index CDI date, avoiding courses that
-------------------	--

	
overlap with extended initial CDI treatment regimens, AND.
 
3. Encompassing all antibiotics separated by up to 72 hrs linked into the same course, AND4. Ending with the first episode of CDI relapse, as all concurrent (started within 48HR of recurring C. difficile symptoms) and subsequent antibiotic courses are excluded from further analysis 
A course with CDI prophylaxis is defined as:
 
1. Having concurrent use of either metronidazole (intravenous or oral) or oral vancomycin or fidaxomicin therapy for at least 50-percent of the duration of the high risk antibiotic course, AND2. Having prophylaxis to within 72 hours of the last dose of the high-risk antibiotic agent; thus an extended high risk antibiotic course may have a segment covered by prophylaxis, but if the last 3 days are no longer receiving the potential benefit of prophylaxis, the course is considered to be unprophylaxed. 
A CDI relapse is defined as:
 
1. Attributable to a high risk antibiotic exposure if clinical symptoms and/or positive stool assay developed greater than 48-hours after antibiotic exposure, AND2. Occurring within 8 weeks of completion of the high risk antibiotic course, AND3. Compatible with clinical evidence suggestive of CDI disease during chart review; including a leukocytosis without alternative etiology and responding to CDI treatment, new onset of diarrhea, presence of radiographic or if relevant autopsy evidence of colitis, and/or repeat positive stool assay with appropriate clinical symptoms. If these indicators of CDI were present at the time of antibiotic onset, or within 48hrs, this was deemed a recurrence of infection NOT attributable to the high risk antibiotic course and was omitted from the relapse population. 
The beneficial effects of Bezlotoxumab will be considered to last for the entire 8 week observation period, regardless of the number or timing of antibiotic courses within that period. Analysis of the effects of cumulative exposure to high-risk antibiotics or exposure late in this period will be assessed separately. The effect of subsequent CDI-active antibiotics, while excluded within 24 hrs of Bezlotoxumab dosing but potentially used within the Bezlotoxumab therapeutic window, will also be considered in secondary analyses (intent-to-treat).
 
LABORATORY INVESTIGATION
 
Using a C. difficile toxigenic culture well-established in the laboratory of the PI (referenced in Boyanton, 2012), stool will be collected by rectal swab from consented subjects in the Bezlotoxumab arm. If subsequent stool samples are sent to our clinical microbiology laboratory for any reason, they are routinely held for 5 days and would be available for C difficile toxigenic culture. Isolated organisms can be comparatively typed by the multi-locus variable number tandem repeat methodology (Marsh, 2007) with great variability in the 3 amplified PCR product sizes. Common letters (below) reflect isolates from neighbor pairs (same ward, same week) albeit each column is a unique patient.

--	---

	 L A A B B C C D D E E F F G G H H H L	
2.6 Study Duration	
Estimate of 1 year required to recruit 50 patients (from an estimated 150 eligible) and another 6 months to complete the study analysis. A computer simulation indicates there should be 150 eligible subjects in 1 year. Of these, ~50 will be on prophylaxis and ~50 will decline participation and will be followed as no prophylaxis controls.
	
2.7 Statistical Analysis and Sample Size Justification	
The PI and local statistician will be responsible for analyzing the study data.
 
Variables/Time Points of Interest
 
The primary outcome variable is relapse of CDI within 8 weeks of study entry. Secondary outcomes are relapse of CDI within 4 weeks of study entry (the interval with highest protective antibody levels), all-cause mortality, time to relapse and duration of hospitalization.
 
Baseline variables collected for each subject include : age, gender, number/dates/treatment of prior CDI episodes, current PPI use and H2-blocker use, Charlson score, immunosuppression, Inflammatory Bowel Disease or Irritable Bowel Syndrome, use of cathartics/lactulose, and indication for current antibiotics.
 
Variables related to the past CDI episode include markers of disease severity : WBC, fever >100.5°F, creatinine, albumin – to generate a Zar score (Zar,2007)
 
Statistical Methods
 
The analysis population is the per-protocol population, with 2 major comparator groups – those receiving Bezlotoxumab and those with no prophylaxis. The latter will be comprised of 3 subgroups – the control group from the Wong study and 2 concurrent observation groups- a PASSIVE followup group of subjects undergoing chart review , and an ACTIVE followup group of subjects declining study drug but agreeing to phone followup at 8 weeks. All groups will be compared across baseline parameters cited above. Risk factors pre-specified for recurrent CDI include age, immunocompromise, and severe CDI will be compared across groups, and tested for associations for the major outcomes of CDI relapse and mortality at 4 weeks and 8 weeks.
 
In the Wong study, there was a remarkably equal distribution of variables among the
	

[figure not shown]
antibiotic prophylaxis and no prophylaxis groups. We similarly expect no imbalance between our current study and observation groups in terms of risk factor distribution, though self-selection bias will be considered at the interim analysis after 30 intervention patients are enrolled.

Categorical variables will be compared using chi-square and Fisher's Exact analysis and continuous variables will be compared using Mann-Whitney analysis, with $p < 0.05$ considered to be significant.

In survival analysis (Kaplan-Meier), time to CDI relapse is defined from the date of bezlotoxumab study dosing or study refusal - to the date of relapse and limited by a maximum observable window of 8 weeks from the dose of bezlotoxumab. Subjects are censored on the date of death, if death occurred within the observable window, or at the beginning of a new potential antibiotic prophylaxis course (i.e.. If within the 8 week observation period there is receipt of metronidazole, oral vancomycin or fidaxomicin.) or receipt of fecal microbiota transplant. A Cox proportional hazards model will be used for group comparison when adjusting for covariates.

The survival analysis from the Wong study, demonstrating the benefits of antibiotic prophylaxis on preventing relapsed CDI, is summarized in the following figure:

Relapse Free Duration

For the second objective, rates of CDI relapse will be compared among study subjects with or without *C. difficile* colonization at study entry. This is an exploratory study to inform future studies. It is expected that 20% of subjects will be colonized at study entry (based on Sunkesula, 2013) –the expected number of these that relapse is unknown, as data is conflicting on whether colonization is protective or predictive of relapse.

Power/Sample Size:

Estimates of group size and expected antibiotic prophylaxis outcomes are derived from the Wong and Van Hise studies which have similar or nearly identical design to the current proposal, albeit retrospective. In the Wong study, of 248 enrolled subjects, 104 received prophylaxis with metronidazole (n=63 total, 19 combined with vancomycin) or vancomycin (n=60), and 144 did not. In this latter group, 86 were \geq 60 yrs old of whom 23 relapsed, for a relapse rate of 26.7%. For the bezlotoxumab arm, the expected benefit is between a 43-54% reduction in relapse incidence (Gerdinger, 2018), with the variability based on the number of risk factors for CDI relapse in our population – all have at least 1 risk factor : most with age >65 and all with concurrent high-risk antibiotics. The expected CDI relapse rate in the active arm is therefore 12.2-15.2%. Thus

1. We need 62 bezlotoxumab subjects (at 12.2% relapse) to be 80% powered to detect a difference in outcomes vs. the no prophylaxis control population (with a relapse rate of 26.7%), with a two-tailed alpha=0.05.
2. We need 103 bezlotoxumab subjects (at 15.2% relapse) to be 80% powered to detect a difference in outcomes vs. the no prophylaxis control population (with a relapse rate of 26.7%), with a two-tailed alpha=0.05.

In 1 year, we expect 50 bezlotoxumab subjects and 50 no-prophylaxis controls in the prospective cohort. The numbers of subjects in the no-prophylaxis observational arms can be supplemented by retrospective chart reviews incorporating the same analysis used in the prospective study, or by merging with the control arm of the Wong study.

Given the prospective design, with more data available regarding relapse than in the Wong study (wherein outpatient records were not yet electronic) and the fact that relapse rates in the control group in the MODIFY studies were 39% in those over 65, its possible that more relapses will occur in the no-prophylaxis group than the 26.7% expected. This would lower the numbers needed to show a significant benefit. An interim analysis is planned after 6 months or 30 subjects enrolled, to re-assess realistic timelines for achieving significant results from this project. Notably, this is a pilot study which if it meets targets, could potentially be extended by 3 to 6 months to achieve statistically significant power. Alternatively, if study effects exceed expectations, a placebo-controlled design could be considered moving forward- for the pilot study, this is precluded by the larger sample size anticipated for such a project.

2.8 Specific Drug Supply Requirements	
The Bezlotoxumab drug supplies will be open label and provided by MSD.
 
The institution's research pharmacy will require bulk supplies from MSD (one large container of 10 courses at 1 time). As bulk supplies are provided by MSD, our institution's pharmacy will be responsible for preparing individual patient doses. A description as to how the clinical supplies are to be packaged and labeled for each patient will be added to the protocol.
 
Note: At conclusion of the study or upon drug expiration, the MSD GRS will be responsible for issuing a Drug Disposition Letter to the investigator for US based studies.
 
The investigator will be responsible for the destruction of the supplies at the study center pursuant to the ICH/GCP Guidelines, local regulations and the investigator's institutional policies. Clinical supplies will be received by a designated person (research pharmacist) at the study site, handled and stored safely and properly, and kept in a secured location to which only the investigator and designated assistants have access. Clinical supplies are dispensed in accordance with the protocol. The investigator is responsible for keeping accurate records of the clinical supplies, the amount dispensed to and returned by the patients, and the disposition at the end of the study.

2.9 Adverse Experience Reporting	
The study agreement will outline the requirement for adverse experience reporting. The Model Study Agreement will be used. Tolerability of study drug will be assessed with longitudinal assessments/chart reviews. Any adverse events during infusion will be recorded and any deaths or serious events leading to prolonged hospitalization or readmission (potentially ascribed to the study drug) in the subsequent 30 days will be reported to our local IRB and the FDA MedWatch.
 
All active study subjects will be queried at 1 day, 4 weeks and 8 weeks after enrollment for any change in their health status reflecting potential safety concerns related to receipt of study drug. Though not a primary focus of this research, any Serious Adverse Events will be tabulated and reported to the IRB, and Suspected Unexpected SAE's (SUSAR) will be reported to the FDA.
 
A Safety Officer will be designated (an ID physician who is not part of the study team) to review all SAE's after 12 and 25 (of 50 planned) subjects have been enrolled, and together with a statistician, determine if there are serious safety concerns related to the study drug requiring modification or termination of the study protocol.

2.10 Itemized Study Budget	
A preliminary study budget is provided with the initial proposal submitted to give guidance to the MISP Review Committee as to the expected study costs. A refined itemized budget detailing the costs associated with the study will be provided with the final protocol or included in the study agreement as Exhibit B.

2.11 References	
 
Boyanton, Jr., B L, P Sural, CR. Loomis, C Pesta, L Gonzalez-Krellwitz, B Robinson-Dunn and [name]. (2012) ,Loop-Mediated Isothermal Amplification Compared to Real-time PCR and Enzyme Immunoassay for Toxigenic C. difficile Detection. Journal of Clinical Microbiology, 50(3):640-45

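### The 24-hour entry rule for CDI-active drugs is not aligned with the course-based prophylaxis definition, so a patient can be enrolled and dosed and then leave the primary analysis because of drug given before entry

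*Combined protocol and SAP*

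**What the plan says.** **Entry.** Sections 2.3 and 2.5 share two inclusion criteria that matter here: "Use of high-risk antibiotics for inducing CDI within 72 hrs of enrolment" and "No use of CDI active antibiotics within 24 hrs". The Definitions part of Section 2.5 ties the 24-hour interval to dosing: CDI-active drugs are described as "while excluded within 24 hrs of Bezlotoxumab dosing but potentially used within the Bezlotoxumab therapeutic window". Nothing limits how long the antibiotic course, or CDI-active drug within it, has already run.

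**Rescreening.** Under Subject Identification in Section 2.5, patients found on metronidazole, oral vancomycin or fidaxomicin are held back, and "they will be rescreened for inclusion if further antibiotics are given without concurrent prophylaxis".

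**Course definition.** Section 2.5 builds a high-risk course by "Encompassing all antibiotics separated by up to 72 hrs linked into the same course, AND". A course is prophylaxed if CDI-active drug was used "for at least 50-percent of the duration of the high risk antibiotic course" and it also meets "Having prophylaxis to within 72 hours of the last dose of the high-risk antibiotic agent". An explanatory clause adds that a longer course may be partly covered and still count as unprophylaxed if its last three days are uncovered.

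**Consequence.** Section 2.3: "Patients receiving any such prophylaxis will be excluded from the per-protocol analysis, which will be the primary analysis". The secondary intent-to-treat analysis assigns groups by prophylaxis status at entry only.

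**The concern.** Entry looks back 24 hours, while exclusion from the primary analysis looks at the whole linked course, including the part before entry. If the two are not aligned, three things follow.

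- Study drug can be given to patients whom the primary analysis then discards because of treatment that preceded enrolment.
- When the antibiotic is still running at entry, the stop date decides whether the patient is kept. Two patients identical at entry can be handled differently because one antibiotic ran longer. That is selection on a post-entry event, and Section 2.5 itself plans to examine cumulative high-risk antibiotic exposure as a separate question.
- The same definition decides which decliners count as unprophylaxed controls, so both sides of the primary comparison are affected.

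Section 2.2 cites retrospective studies in which vancomycin and/or metronidazole lowered relapse from 20-27% to 4-8%, and another that found no benefit of oral vancomycin after a first episode. Pre-entry exposure to these drugs cannot simply be assumed irrelevant to the outcome.

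**Working it through.** The plan states no figure for this situation, so there is none to reproduce. The check is whether the entry and exclusion rules can both be met by drug given only before entry.

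**Notation.** Time runs from the first high-risk dose. L is the last high-risk dose of the linked course, P the last CDI-active dose and E entry. Assumptions: prophylaxis starts with the course, and none is given after E.

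**Rules as inequalities**

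- Inclusion 3: E − P ≥ 24 h
- Inclusion 2: high-risk antibiotic within 72 h of E, so L ≥ E − 72 h
- Prophylaxed, part 1: P / L ≥ 0.5
- Prophylaxed, part 2: L − P ≤ 72 h

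**Three schedules (days)**

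| | L | P | E | Free of CDI-active drug at entry | Coverage P/L | Gap L − P | Course counts as |
|---|---|---|---|---|---|---|---|
| A, running at entry | 6 | 4 | 5 | 24 h | 4/6 = 67% | 48 h | prophylaxed |
| B, ended before entry | 6 | 5 | 7 | 48 h | 5/6 = 83% | 24 h | prophylaxed |
| C, as A but longer | 8 | 4 | 5 | 24 h | 4/8 = 50% | 96 h | unprophylaxed |

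All three patients meet inclusions 2 and 3. In B the last high-risk dose was 24 h before entry. A does not depend on the 24-hour boundary: entry at day 5.5 gives 36 h free of drug and the same classification. A and C are identical at entry and differ only in how long the antibiotic continued.

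**How long after entry the antibiotic can run**

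- From inclusion 3 and part 2: L − E = (L − P) − (E − P) ≤ 72 − 24 = 48 h.
- Part 1 gives L − P ≤ L/2, so also L − E ≤ L/2 − 24 h. For a 6-day course this is 72 − 24 = 48 h; for a 4-day course, 48 − 24 = 24 h; for a 2-day course, zero.

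So a course still running at entry becomes prophylaxed on pre-entry drug alone only if it stops within 48 h after entry, or sooner for courses under 6 days. Stepping through all schedules at 12-hour intervals for courses of 2 to 14 days agrees: at least one qualifying schedule exists at every length, and the longest remaining time is 2 days from length 6 upward.

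**Does another passage close the gap?**

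- The rescreening sentence does not say that the further antibiotics must form a new course. Under the linkage rule, a new order within 72 h of the last antibiotic belongs to the same course. A patient first identified after prophylaxis has stopped is not covered by that sentence at all.
- The Definitions text on CDI-active drug within the bezlotoxumab window addresses only later use.
- Censoring in Section 2.7 applies to a new prophylaxis course within the 8 weeks, not to earlier drug.
- The baseline list in Section 2.7 includes treatment of prior CDI episodes, but not CDI-active drug earlier in the current course. Section 2.5 does collect all antimicrobials received.

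**The case against.** **The rules do different jobs.** Inclusion 3 decides who may be dosed; the 50%/72-hour rule classifies a course once it is complete. A reader might infer that they contradict each other. They do not, since both can be applied as written. What stands is a failure to align them.

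**Status is usually not known at screening.** A reader might infer that the plan knowingly enrols patients already destined for exclusion. That is true only of schedule B, where the course ended before entry. The inclusion wording permits this, although the flowchart in Section 2.4 starts from inpatients on antibiotics. In schedule A the status depends on the later stop date.

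**The screening step helps.** Patients on prophylaxis are deferred, and a new order is a natural reading of the rescreening sentence. This makes the case less common but does not exclude it, for the reasons given above.

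**Partial coverage is tolerated on purpose.** Section 2.3 adopts the historical study's standard so that comparison with its groups is possible, and Section 2.5 says openly that a partly covered course may count as unprophylaxed. That choice is legitimate and is not challenged here. It also means that a stricter entry rule would move the prospective cohort slightly away from the historical controls.

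**Three further inferences are unsupported.** CDI-active drug that is the tail of CDI treatment does not create the same problem, because the valid-course definition avoids courses overlapping extended initial treatment. Nothing in the documents says that recent vancomycin or metronidazole suppresses the entry culture. And no figure for a shrunken bezlotoxumab arm can be derived: Section 2.6 counts the roughly 50 patients on prophylaxis apart from the 50 recruits, so patients who cross over may add to the recruits rather than deplete them.

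**Conclusion.** The point holds as a misalignment. A patient can satisfy every entry rule, receive bezlotoxumab, and be removed from the primary per-protocol set solely because of CDI-active drug given before entry. For courses still running at entry, removal hinges on whether the antibiotic stops within about 48 h afterwards.

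The size is unknown. The source pool is the roughly 50 of 150 eligible patients whom Section 2.6 expects to be on prophylaxis. The documents do not say how many stop mid-course and then enrol or decline; the number may be small, possibly zero. For scale, each treated patient lost from the primary set is 1/50 = 2% of the expected arm, and Section 2.7 already expects 50 against a stated need of 62 or 103. The secondary intent-to-treat analysis would probably keep these patients, which limits the damage but does not protect the primary result.

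The conclusion rests on reading the prophylaxis definition over the whole linked course, as written. The examples avoid courses with exactly three uncovered days, where the 72-hour limit and the explanatory clause could be read differently. It is worth correcting because the change is cheap.

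**What to change.** Reconcile inclusion 3 and the rescreening sentence (Sections 2.3 and 2.5) with the course definition, so that one linked-course definition governs both entry and exclusion from the primary analysis:

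- State that further antibiotics, for rescreening, means a new course under the plan's own 72-hour linkage rule, and that inclusion 3 is read against that same course. This should also cover patients first identified after prophylaxis has stopped. CDI-active drug given before entry then cannot by itself trigger primary exclusion.
- Apply the same rule to concurrent decliners, with the date of refusal as their entry point.
- Add CDI-active drug given before entry to the baseline variables in Section 2.7.
- Do not add a new washout length; the documents give no basis for one.

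**Cost.** Protocol wording and one baseline item, using medication records already reviewed. A few patients who stop prophylaxis mid-course will wait for a later course or not be enrolled. The prospective entry rule also becomes slightly stricter than the one behind the historical controls, and the plan should say so where that comparison is described.
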